#### **3.3.2. Population-level Safety Stopping Rules**

The DMC, as part of continuous monitoring of safety, will evaluate the data across the study for the following criteria:

- One active-treated subject experiences an AE of severe intensity (eg, severe injection site reaction, severe allergic reaction, etc) that is related to the study drug OR two active-treated subjects experience the same AE of moderate intensity that is related to the study drug.
- One active-treated subject with ALT or AST  $>5 \times$  ULN or serum total bilirubin  $>2 \times$  ULN.

If any of the above criteria are met, an in-depth review of data will be conducted by the DMC, and one of the following recommendations will be made:

- To continue with the study as planned, with no change
- To continue with the study as planned, with modification to the safety monitoring plan
- To continue with the study, but at a reduced dose
- To terminate the study

## **4. STUDY POPULATION**

The patients must sign and date the Informed Consent Form (ICF) provided by the study site before any study-specific qualification procedures are conducted.

### **4.1. Inclusion Criteria**

#### **4.1.1. Screening**

Patients must satisfy all of the following criteria to be included in the study:

1. Male or female patients aged 18 to 65 years with clinical diagnosis of NS including at least 3 out of the 4 following clinical criteria:
    - Neonatal erythroderma
    - Bamboo hair and/or alopecia
    - Chronic atopy specified as food allergy and/or asthma and/or rhino-conjunctivitis and/or eczema for at least 2 years
    - Ichthyosis linearis circumflexa or scaling erythroderma or equivalent
- Eligible patients are those who have received ineffective or otherwise inappropriate standard-of-care treatment and therefore remain in need of cure.
2. Immunohistochemistry documentation of absence of LEKTI in the skin or confirmed SPINK5 gene mutations.
  3. NS involvement of  $\geq 20\%$  of Body Surface Area (BSA).
  4. Patients must give written informed consent to participation in the study prior to Screening.
  5. Patients must be willing and able to understand and comply with study requirements.
  6. Patients must be willing to have skin tape harvests collected from lesional and non-lesional skin areas.
  7. All women must have a negative serum pregnancy test at Screening. Women must not be lactating.
  8. Women of childbearing potential (ie, a female after menarche and before becoming postmenopausal [no menstrual period for a minimum of 12 months without a medical cause alternative to natural menopause] or being made permanently sterile by surgery [hysterectomy, bilateral salpingectomy, or bilateral oophorectomy] done at least 1 month before the first dose of study drug) with a male partner must be willing to practice effective contraception during the study, starting at Screening and continuing for 3 months after the last dose of study drug. Methods of highly effective contraception include 1) hormonal administration of estrogen and progestogen combined, which may be given in oral, intravaginal, or transdermal form, or of progestogen only, which may be given in oral, injectable, or implantable form; 2) use of intrauterine devices, including intrauterine hormone-releasing devices; 3) bilateral tubal occlusion; 4) vasectomy of partner; and 5) complete sexual abstinence.

#### **4.1.2. Baseline (Main Phase-Interventional Part)**

At Week 1 Baseline Visit, patients must continue to satisfy all of the following criteria before continuing to the Interventional Part of the study:

1. NS involvement of  $\geq 20\%$  of BSA. Eligible patients are those who have received ineffective or otherwise inappropriate standard-of-care treatment and therefore remain in need of cure.
2. All women must have a negative urine pregnancy test at Baseline. Women must not be lactating.
3. Women of childbearing potential (ie, a female after menarche and before becoming postmenopausal [no menstrual period for a minimum of 12 months without a medical cause alternative to natural menopause] or being made permanently sterile by surgery [hysterectomy, bilateral salpingectomy, or bilateral oophorectomy] done at least 1 month before the first dose of study drug) with a male partner must be willing to practice effective contraception during the study, starting at Screening and continuing for 3 months after the last dose of study drug (refer to Section 4.1.1 for methods of highly effective contraception).
4. Patients must agree not to participate in any other investigational study during study drug administration and for 3 months after the last dose of study drug.

#### **4.2. Exclusion Criteria**

##### **4.2.1. Screening**

Patients who meet any of the following criteria will be disqualified from entering the study:

1. Any skin disease that may interfere with the diagnosis or evaluation of NS.
2. Any infection requiring treatment with systemic antibiotics, antivirals, antiparasitics, or antifungals within 2 weeks before Screening visit.
3. Concomitant systemic disease not controlled by treatment. Stability for 3 months prior to Screening is required.
4. Kidney or liver disease with significant impairment of organ function (creatinine clearance  $< 30$  mL/min, calculated using the Cockcroft-Gault Equation, and Child-Pugh Class C; ALT and AST  $\geq 2 \times$  ULN range; total bilirubin  $\geq 1 \times$  ULN).
5. Concomitant disease or condition that may interfere with, or treatment of which may interfere with, the conduct of the study or that would, in the opinion of the investigator, pose an unacceptable risk to the patient in this study.
6. Any significant condition (eg, medical, psychiatric, or social) that according to investigator's judgment would prevent compliance with study protocol and full study participation.
7. Known hypersensitivity to any ingredient of the study drug product.
8. Anticipation of the need for surgery or hospitalization during the study.

9. History of suicide attempt or suicidal ideation within 1 year prior to Screening.
10. History of substance abuse within 6 months prior to Screening or a positive urine drug test at Screening. Medical marijuana may be used per discretion of the investigator.
11. History or positive test result for human immunodeficiency virus (HIV) at Screening.
12. Active hepatitis B virus (HBV) infection, determined by positive test result for hepatitis B surface antigen, at Screening.
13. Active hepatitis C virus (HCV) infection, determined as HCV ribonucleic acid (RNA) above the limit of detection in patients with positive HCV antibody titer, at Screening.
14. Use of topical drugs that may alter the course of NS (eg, topical corticosteroids and topical calcineurin inhibitors) within 2 weeks before Screening or anticipation of need to use these drugs during study drug.
15. Systemic treatment with corticosteroids, immunosuppressants, targeted therapeutics, biologics, and IV Ig within 4 weeks before Screening.
16. Participation in any other clinical study or expanded access program with an investigational drug or device within 4 weeks before Screening.
17. Suspected or confirmed COVID-19 within 4 weeks before or ongoing at Screening and planned vaccination against COVID-19 during study drug.

#### **4.2.2. Baseline (Main Phase-Interventional Part)**

At Week 1 Baseline Visit, patients must continue to not meet any of the following criteria before continuing to the Interventional Part of the study:

1. Any infection requiring treatment with systemic antibiotics, antivirals, antiparasitics, or antifungals within 2 weeks before Baseline visit.
2. Concomitant disease or condition that may interfere with, or treatment of which may interfere with, the conduct of the study or that would, in the opinion of the investigator, pose an unacceptable risk to the patient in this study.
3. Any significant condition (eg, medical, psychiatric, or social) that according to investigator's judgment would prevent compliance with study protocol and full study participation.
4. Anticipation of the need for surgery or hospitalization during the study.
5. Use of topical drugs that may alter the course of NS (eg, topical corticosteroids and topical calcineurin inhibitors) within 2 weeks before Baseline or anticipation of need to use these drugs during study drug.
6. Systemic treatment with corticosteroids, immunosuppressants, targeted therapeutics, biologics, and IV Ig within 4 weeks before Baseline.
7. Participation in any other clinical study or expanded access program with an investigational drug or device within 4 weeks before Baseline.
8. Suspected or confirmed COVID-19 within 4 weeks before or ongoing at Baseline and planned vaccination against COVID-19 during study drug.

## 5. STUDY DRUG

### 5.1. Assigning Patients to Treatment Group(s)/Sequences and Blinding

#### 5.1.1. Treatment Group

The patients will either receive DS-2325a or placebo.

#### 5.1.2. Method of Treatment Group(s)/Sequences Allocation

Randomization will follow a randomization schedule generated by an independent biostatistician. Patients, investigators, and site staff will be blinded, except for the unblinded site pharmacist or designee who will be responsible for preparing the study drugs. Sponsor's staff or representative (eg, clinical research organization) will also be blinded, except for the unblinded monitor.

#### 5.1.3. Blinding

The Interventional Part Main Phase will be double-blinded.

Blinding will be applied to all personnel related to the study (patients, investigators, and Sponsor), with the exception of the independent biostatistician and other staff involved in the preparation, release, and shipment of study drug.

The independent biostatistician will generate the randomization schedule in accordance with the operating procedure for allocating study drug. Until the study is unblinded, the study drug randomization schedule will be kept securely.

Preventive measures will be taken to ensure that the blinded team is not unblinded.

#### 5.1.4. Emergency Unblinding Procedure

In the case of an emergency where, in the opinion of the investigator, discontinuation of study drug is not sufficient and the study drug must be unblinded in order to evaluate further a course of medical treatment, the investigator can perform the unblinding by opening the paper envelopes stored at the study site. Entry of the adverse event electronic case report form (eCRF) page should be completed before unblinding except in cases where immediate treatment of the patient is required. If immediate treatment is required, the adverse event eCRF page is to be completed within 24 hours of the unblinding.

In the event of an emergency unblinding, the patient will be informed about their treatment assigned. Information about the treatment assignment **must be** restricted to designated study site staff/personnel who are providing immediate care to the patient. Any documentation of the treatment assignment **must be** maintained separately (ie, a secured file). The information **must not be** included in the patient's source files to ensure the treatment assignment will remain blinded to study personnel not involved with the patient's immediate care.

Once the study drug has been unblinded for a specific patient, investigator should consult Sponsor on whether discontinuing treatment for the patient. If discontinuation is confirmed, the patient should leave the study drug phase. The end of treatment and follow-up assessments will be performed as defined in the protocol.

## **5.2. Study Drug**

### **5.2.1. Description**

DS-2325a will be provided as a sterile solution in vials of CCI [REDACTED]. Placebo will be prepared from normal saline solution. The appearance of DS-2325a solution is virtually indistinguishable from the appearance of saline. Additional information is available in IB and in the Pharmacy Manual. DS-2325a and placebo will be administered by SC injection, with the exception of the initial (“loading”) dose, which will be administered by IV infusion.

### **5.2.2. Labeling and Packaging**

DS-2325a will be supplied by the Sponsor. Saline placebo may be sourced locally or provided by Sponsor/Contract Research Organization (CRO). DS-2325a will be labeled in compliance with regulatory requirements and packaged. The packaging will be clearly labeled “For Clinical Trial Use Only” and will display name of the study drug, the lot number, storage condition, protocol number, and other required information as applicable in accordance with local regulations.

### **5.2.3. Preparation**

Preparation of the study drug is detailed in the Pharmacy Manual.

### **5.2.4. Administration**

Treatment will be administered by CCI [REDACTED]

[REDACTED] Permitted injection sites are the abdomen, upper arm, and/or thigh (more than one injection site may be used simultaneously).

Preparation and administration instructions will be provided in the Pharmacy Manual.

### **5.2.5. Storage**

DS-2325a and placebo must be stored in a secure, limited access storage area under the labeled storage conditions.

If storage conditions are not maintained per specified requirements, the Sponsor or CRO should be contacted.

### **5.2.6. Drug Accountability**

When study drug shipment is received, the investigator or designee will check the amount and condition of the drug against the shipping documentation.

In addition, the investigator or designee shall contact Sponsor as soon as possible if there is a problem with the shipment.

Drug Accountability will be provided for study drug and the placebo control. The record must be kept current and should contain the dates and quantities of study drug received, patient's (identification number and/or initials or supply number as applicable) for whom the study drug was dispensed, the date and quantity of study drug dispensed and remaining, as well as the initials of the dispenser.

At the end of the study, or as directed, all study drug and placebo, with all discrepancy resolved, including unused, partially used, or empty containers, will be locally destroyed or returned to a designee as instructed by Sponsor. Study drug will be destroyed or returned only after the study monitor has completed a final inventory to verify the quantity to be returned. The return of study drug must be documented, and the documentation included in the shipment. At the end of the study, a final study drug reconciliation statement must be completed by the investigator or designee and provided to the Sponsor. Unused drug supplies may be destroyed by the investigator when approved in writing by the Sponsor and the Sponsor has received copies of the study site's drug handling and disposition standard operating procedures (SOPs) and it is assured that the Sponsor will receive copies of the certificate of destruction which is traceable to the study drug.

#### **5.2.7. Retention Samples**

No retention of samples is required for storage at the investigational site.

### **5.3. Control Treatment**

In the Interventional Part Main Phase, patients will be randomized to 2 parallel arms to receive DS-2325a or placebo in a 2:1 ratio. Placebo will be prepared from normal saline solution.

### **5.4. Dose Interruptions**

Protocol prescribed dosing schedule should be followed throughout the entire study. In case a patient misses a scheduled visit and thereby a dose, the dose should be administered at the next visit. Any such dose interruptions should be discussed with the Sponsor and documented. After any dose interruption, the patient should resume the dosing schedule as soon as possible.

### **5.5. Method of Assessing Treatment Compliance**

All the patients will receive study drug administration under the supervision at the study site. The timing of the administration and the amount administered will be recorded.

### **5.6. Concomitant Medications**

#### **5.6.1. Concomitant and Prohibited Medications**

Emollients and topical keratolytic agents and oral antihistamines are allowed. Systemic antibiotic therapy to treat possibly emerging skin infections is allowed.

The following medications are prohibited:

- Systemic corticosteroids, immunosuppressives, targeted therapeutics, biologics, and IV Ig.

- Topical corticosteroids and other topical immunosuppressive agents, including topical calcineurin inhibitors. However, some occasional and temporary use of topical corticosteroids may be allowed only with the intent of symptom relief and if it is not deemed by the investigator to be capable to alter NS course and confound the interpretation of study results.

During the study, other concomitant treatment will be given only if deemed strictly necessary by the investigator or co-investigator. In any case, all concomitant treatments will be reported in the eCRF along with their daily dosage, duration, and reasons for administration.

Patients who have received any prohibited concomitant treatment may be withdrawn from the study at the discretion of an investigator.

#### **5.6.2. Dietary and Lifestyle Restrictions**

No restrictions other than limiting alcohol consumption to no more than 14 units per week (one unit of alcohol equals to 250 ml of beer, 100 ml of wine, and 10 ml of spirits).

### **5.7. Patient Withdrawal/Discontinuation**

#### **5.7.1. Reasons for Withdrawal**

Any patient who is withdrawn from the study drug for any reason will have their reasons for withdrawal recorded.

Patients may be withdrawn from the study after signing the ICF for the following reasons:

- Adverse Event
- Withdrawal by Patient
- Physician Decision
- Death
- Lack of Efficacy
- Pregnancy
- Protocol Deviation
- Study Terminated by Sponsor
- Lost to Follow-up
- Other

#### **5.7.2. Withdrawal Procedures**

If a patient is withdrawn from the study, the investigator will complete and report the observations as thoroughly as possible up to the date of withdrawal, including the date of last dose of study drug and the reason for withdrawal. The investigator will try to perform EOT and EOS procedures, unless the patient is withdrawn during the Observational Part of the study.

If the patient is withdrawn due to an AE, the investigator will try to follow the patient until the AE has resolved or stabilized.

### **5.7.3. Patient Replacement**

Replacing patients will be permitted during the Observational Part and the Interventional Part Main Phase in order to achieve a minimum of 9 patients for ECS evaluation at the end of the Interventional Part Main Phase. However, a patient withdrawn because of AEs considered related to study drug will not be replaced.

### **5.7.4. Patient Re-screening Procedures**

Re-screening is permitted for any patient who failed to meet eligibility criteria upon initial screening. The patient identification number must remain different at the time of re-screening. The initial screening information and the reason why the patient is ineligible for the initial evaluation will be recorded on the Screening Log. No data from the initial evaluation will be entered into the clinical database for a patient who is rescreened.

## **5.8. Criteria for Discontinuing Study Drug**

Treatment will be temporarily put on hold until further evaluation by the DMC if the subject experiences

- Any event severe in nature (eg, severe injection site reaction, severe allergic reaction, etc) deemed by the DMC as necessitating further safety review before treatment can be continued
- Hy's Law event: ALT or AST  $\geq 3 \times$  ULN with simultaneous total bilirubin  $\geq 2 \times$  ULN)
- QTc prolongation: QTcF  $> 500$  msec OR increase in QTcF from pre-dose baseline of  $> 60$  msec

After an in-depth review of the safety data is conducted by the DMC, the decision to either continue with treatment as planned, to continue treatment, but at a reduced dose, or to terminate participation in the study will be made. If the decision is made to continue treatment, but at a reduced dose, the guidelines as specified in the dose reduction section of the protocol will be followed.

In addition, the subject will be discontinued from the study

- If a subject experiences a severe event or abnormal laboratory test result that the investigator deems to pose a safety risk if he/she were to continue in the study.
- If the use of prohibited medications such as topical corticosteroids and other topical immunosuppressive agents, including topical calcineurin inhibitors, or systemic corticosteroids, immunosuppressives, targeted therapeutics, biologics, and IV Ig is deemed necessary in the opinion of the investigator, the subject may be withdrawn to avoid biased interpretation of study results.
- If a subject shows worsening disease or lack of efficacy according to the discretion of the investigator.

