### **3.3. Stopping Rules**

#### **3.3.1. Subject-level Safety Stopping Rules**

For any subject experiencing the following events, treatment will be suspended until further evaluation by the Data Monitoring Committee (DMC).

- Any event severe in nature (eg, severe injection site reaction, severe allergic reaction, etc) deemed by the DMC as necessitating further safety review before treatment can be continued
- Hy's Law event: Alanine aminotransferase [ALT] or aspartate aminotransferase [AST]  $\geq 3 \times$  upper limit of normal [ULN] with simultaneous total bilirubin  $\geq 2 \times$  ULN)
- QTc prolongation: QT interval corrected with Fridericia's formula (QTcF)  $> 500$  msec OR increase in QTcF from pre-dose baseline of  $> 60$  msec

After an in-depth review of subject-level data is conducted by the DMC, one of the following recommendations will be made:

- To continue with treatment as planned
- To continue treatment, but at a reduced dose
- To terminate participation in the study

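### Permanently stopping study drug means leaving the study, so a Main Phase patient discontinued by the investigator after a last dose at Week 9 or earlier has no planned Week 13 IASI, IGA or PRO

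*Combined protocol and SAP*

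**What the plan says.** **Investigator route.** Section 5.8 lists investigator criteria under the words "In addition, the subject will be discontinued from the study". They cover a severe event or abnormal laboratory result judged to be a safety risk, a need for prohibited medication (here the patient only may be withdrawn), and this: "If a subject shows worsening disease or lack of efficacy according to the discretion of the investigator". Section 5.6.1 repeats the medication criterion as a discretionary one: "Patients who have received any prohibited concomitant treatment may be withdrawn from the study at the discretion of an investigator".

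**DMC route.** Under 3.3.1 treatment is first suspended. The DMC may then recommend continuing, continuing at a lower dose, or "To terminate participation in the study". Neither 3.3.1 nor 5.8 offers stopping drug while remaining in the study.

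**After exit.** Section 5.7.2 says: "The investigator will try to perform EOT and EOS procedures, unless the patient is withdrawn during the Observational Part of the study". Footnote 2 of the Schedule of Events places IASI, IGA and PRO at EOT but not at EOS.

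**Places that mention leaving drug separately.** Section 5.7.1 says: "Any patient who is withdrawn from the study drug for any reason will have their reasons for withdrawal recorded". After emergency unblinding, 5.1.4 says: "The end of treatment and follow-up assessments will be performed as defined in the protocol". Neither keeps the patient on the remaining Main Phase evaluations.

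**What is not an exit.** Section 5.4 covers missed doses: "After any dose interruption, the patient should resume the dosing schedule as soon as possible". Dose reduction (5.9) and holds awaiting the DMC also leave the patient in the study.

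**Analysis.** Section 10.4.4 summarizes change to each post-treatment visit by arm in the mITT set. Section 10.1 plans no imputation in general and leaves further missing-data handling to a separate SAP, which is not among the documents reviewed.

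**The concern.** The Main Phase has one randomized comparison, drug against placebo, in a handful of patients. Sections 3.2 and 10.5 use it, with the pre/post comparisons, to judge whether there is an early clinical signal and whether to continue. If a patient who stops drug also stops being assessed, that patient drops out of the later visit summaries.

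One exit trigger is the efficacy outcome, judged at the investigator's discretion, so the loss can depend on how the patient is doing. A placebo patient who leaves because of poor control makes placebo look better and shrinks the contrast. A drug patient who leaves for the same reason enlarges it. The SAP can choose a rule for missing values, but it cannot supply an assessment that was never made.

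**Working it through.** The plan has no figure to reproduce: the sample size is not based on power and no tests are planned. The check is of visit timing, followed by the size of one loss.

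**Inputs**
- Main Phase doses at Weeks 1, 2, 3, 5, 7, 9 and 11 (Table 1).
- Post-baseline IASI, IGA and PRO before dosing at Weeks 3, 5, 7, 9, 11 and 13 (Tables 1 and 2, footnote 2).
- End of the 12-week Main Phase taken as the Week 13 pre-dose visit. The protocol does not name the visit. TEWL and skin tape have no post-baseline visit before Week 13, which supports this reading.
- EOT timing after early exit is not defined. Two values are used: 1 week after the last dose (3.2), and 2 weeks, as in Table 2 (last dose Week 35, EOT Week 37).
- 9 to 12 patients randomized 2:1, so 6 to 8 on drug and 3 to 4 on placebo.

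**Step 1: exit timing, investigator route.** Exit is assumed to follow the last dose without an intervening hold or missed dose. EOT week = last dose week + 1 or + 2. Evaluations lost are those scheduled after EOT, through Week 13.

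| Last dose (week) | EOT (week) | Evaluations lost |
|---|---|---|
| 1 | 2 or 3 | 6 or 5 |
| 2 | 3 or 4 | 5 or 5 |
| 3 | 4 or 5 | 5 or 4 |
| 5 | 6 or 7 | 4 or 3 |
| 7 | 8 or 9 | 3 or 2 |
| 9 | 10 or 11 | 2 or 1 |
| 11 | 12 or 13 | 1 or 0 |

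With a last dose at Week 9 or earlier, EOT cannot reach Week 13 under either gap. Only a last dose at Week 11 can give an EOT at Week 13. If the Main Phase is taken to end at Week 11, a Week 9 last dose with the 2-week gap gives an EOT at Week 11, so the claim is then limited to a last dose at Week 7 or earlier. EOS, 8 weeks after EOT, sometimes falls near Week 13 (last dose Week 3: Week 12 or 13) but carries no IASI, IGA or PRO.

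**Step 2: DMC route.** Treatment is suspended first, and no time limit is set for the DMC's decision. A patient last dosed at Week 9, held, and terminated after the Week 13 visit has a Week 13 evaluation. The table does not apply here; the loss starts at the termination decision.

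**Step 3: share of an arm lost with one patient.** Placebo: 1/3 = 33.3%, 1/4 = 25%. Drug: 1/6 = 16.7%, 1/8 = 12.5%.

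**Step 4: illustrative upper case for one loss.** If the patient lost is the worst in the arm and changes are normal, the observed arm mean improves on average by E[max of n standard normals]/(n − 1), in SD units:
- n = 3: 0.846/2 = 0.42
- n = 4: 1.029/3 = 0.34
- n = 6: 1.267/5 = 0.25
- n = 8: 1.424/7 = 0.20

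**Step 5: chance of at least one permanent stop.** The documents give no rate. For assumed rates p of 5%, 10% and 20% per patient, 1 − (1 − p)^n is 37%, 61% and 87% for n = 9, and 46%, 72% and 93% for n = 12. These include stops after the Week 11 dose, where no evaluation may be lost, so they overstate the chance of a missing Week 13 value.

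**The case against.** **The decision rule is unharmed.** A reader might infer that exits could tip the ECS rule. With 6 on drug, 2 exits and 2 responders, 2/6 = 33% fails while 2/4 = 50% passes; with 8 on drug, 2 exits and 3 responders, 3/8 = 37.5% fails while 3/6 = 50% passes. The documents do not support that reading. Sections 3.2 and 10.1 count treated patients, the mITT set keeps everyone dosed, and nothing restricts the denominator to patients with a value. This objection stands.

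**Not every stop fits the cut-off.** A reader might apply the Week 9 limit to all permanent stops. DMC terminations come out of a hold, so it does not apply to them. This stands too.

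**EOT captures the outcome.** Where it is done, EOT records the poor result, so the patient does not lack every post-baseline value. But EOT is best effort and earlier than Week 13, and 10.4.4 compares arms visit by visit. Replacement under 5.7.3 restores a count, not that patient's outcome, and is barred after drug-related AEs.

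**Flares need not trigger exit.** Section 1.1 says flares may come every 1 to 2 months, and it is tempting to infer that an ordinary flare would remove a patient. The documents do not show that. Section 5.6.1 allows emollients, keratolytics, antihistamines and some occasional topical corticosteroid use, and the Observational Part shows the investigator each patient's usual course. Discretion leaves the possibility open but gives no rate.

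**Later values may reflect rescue.** This is a fair warning about the remedy. If off-drug IASI were collected without a rule, a fall caused by prohibited rescue could be counted as an ECS response. The remedy must rule that out.

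**Conclusion.** The point holds within limits. Permanent discontinuation under 5.8, or by DMC termination under 3.3.1, is withdrawal from the study, and nothing in the protocol keeps such a patient on the Main Phase clinical evaluations. For investigator-route exits, a last dose at Week 9 or earlier leaves no planned Week 13 IASI, IGA or PRO. That rests on Week 13 as the end of the Main Phase and EOT 1 or 2 weeks after the last dose; with Week 11 as the end, the limit is a last dose at Week 7.

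The firm size is the share of an arm: one loss is 25% to 33% of placebo or 12.5% to 17% of drug. The SD shifts and stop probabilities are illustrative upper cases on assumed inputs. A reader might infer a bias in favour of the drug; the documents do not support a direction, since it depends on which arm loses the patient. No error in the ECS rule and no safety problem is claimed. How far the visit summaries suffer also depends on a SAP not seen here. In an exploratory trial without formal tests, this is a cheap improvement.

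**What to change.** In 3.3.1, 5.7.2 and 5.8, separate stopping study drug from withdrawing from the study. Main Phase patients who stop drug permanently and still consent keep the IASI, IGA and PRO visits already scheduled through Week 13, with time off drug and rescue use flagged. Stopping criteria, EOT and EOS stay as they are.

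Add two analysis statements:
- For ECS, a patient who permanently stopped drug or used prohibited rescue before the end of the Main Phase is a non-responder, whatever the later IASI.
- Off-drug and post-rescue values enter the by-arm visit summaries, which are shown with and without them.

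The cost is at most six extra evaluation visits for one patient (last dose at Week 1: Weeks 3, 5, 7, 9, 11 and 13) and a protocol amendment with updated consent. The visit burden is real, since it already drove the change to biweekly dosing. No new staff, site or procedure is needed.
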